8.2. Safety Assessments

For each patient, ECGs, vital signs, laboratory tests, and other tests should be collected as shown in the SoA (Section 1.3). Results from any clinical laboratory test analyzed by a central laboratory (refer to Appendix 2) will be provided to investigative sites by Lilly or its designee.

Refer to Section 8.3 for details on the recording of AEs.

Lilly will periodically review evolving aggregate safety data within the study by appropriate methods.

Serious adverse events will CCI as soon as they are reported. Cumulative SAEs, reasonably anticipated SAEs, and relevant literature will be reviewed at least quarterly by CCI. Safety findings (including new preclinical data), will be reviewed by a broader group (CCI) on a regular basis. Serious safety findings can be escalated to an independent internal safety review committee.

8.2.1. Clinical Safety Laboratory Assessments

- Lilly or its designee will provide the investigator with the results of safety laboratory tests analyzed by a central vendor, if a central vendor is used for the clinical trial.
- See Appendix 2 for the list of clinical laboratory tests to be performed and to the SoA (Section 1.3) for the timing and frequency.
- The investigator must review the laboratory report, document this review, and record any clinically relevant changes occurring during the study in the AE section of the CRF. The laboratory reports must be filed with the source documents. Clinically significant abnormal laboratory findings are those which are not associated with the underlying disease, unless judged by the investigator to be more severe than expected for the participant's condition.
- All laboratory tests with values considered clinically significantly abnormal during participation in the study or until the completion of Visit 801 after the last dose of study intervention should be repeated until the values return to normal or baseline or are no longer considered clinically significant by the investigator or medical monitor.
 - If such values do not return to normal/baseline within a period of time judged reasonable by the investigator, the etiology should be identified and the sponsor notified.
 - All protocol-required laboratory assessments, as defined in Appendix 2, must be conducted in accordance with the laboratory manual and the SoA (Section 1.3).

If there is an abnormal laboratory value or abnormal value for any other diagnostic or screening test (for example, blood pressure increased or neutrophils decreased) and it is known to be related to a disease diagnosis (for example, hypertension or neutropenia) this should be reported in the CRF as an AE. Do not enter the test abnormality, enter the disease diagnosis or categorical term. If laboratory values from non-protocol-specified laboratory assessments performed at the institution's local laboratory require a change in participant management or are considered clinically significant by the investigator (for example, SAE or AE or dose modification), then the event(s) must be reported in the CRF as AE(s).

8.2.1.1. Immunogenicity Assessment

Where local regulations and ethical review boards (ERBs) allow, blood samples for immunogenicity testing will be collected to determine antibody production against LY3435151 as specified in the SoA (Section 1.3).

At the visits and times specified in the SoA (Section 1.3), venous blood samples will be collected to determine antibody production against the investigational product. To interpret the results of immunogenicity, a venous blood PK sample will be collected at the same time points to determine the plasma concentrations of LY3435151. All samples for immunogenicity will be taken pre-dose. In the event of drug hypersensitivity reactions (immediate or non-immediate), additional blood and urine samples will be collected as close to the onset of the event as possible, at the resolution of the event, and 30 days following the event to evaluate antidrug antibodies (ADA), PK, and additional exploratory biomarkers of hypersensitivity, which could include tryptase, complement levels, and cytokine measurements. Instructions for the collection and handling of blood samples will be provided by the sponsor. The actual date and time (24-hour clock time) of each sampling will be recorded.

Treatment-emergent antidrug antibodies (TE-ADA) are defined in Section 9.4.6.

Immunogenicity will be assessed by a validated assay designed to detect ADA in the presence of the investigational product at a laboratory approved by the sponsor. Antibodies may be further characterized and/or evaluated for their ability to neutralize the activity of the investigational product.

Samples will be retained for a maximum of 15 years after the last patient visit, or for a shorter period if local regulations and ERBs allow, at a facility selected by the sponsor. The duration allows the sponsor to respond to future regulatory requests related to LY3435151. Any samples remaining after 15 years will be destroyed.

8.2.1.2. Hepatic Safety Monitoring

If a study participant experiences elevated alanine aminotransferase (ALT) $\geq 3 \times$ upper limit of normal (ULN), alkaline phosphatase (ALP) $\geq 2 \times$ ULN, or elevated total bilirubin (TBL) $\geq 2 \times$ ULN, liver testing (Appendix 4) should be repeated within 3 to 5 days including ALT, aspartate aminotransferase (AST), ALP, TBL, direct bilirubin, gamma-glutamyl transferase, and creatine kinase to confirm the abnormality and to determine if it is increasing or decreasing. If the abnormality persists or worsens, clinical and laboratory monitoring should be initiated by the investigator and in consultation with the study medical monitor. Monitoring of ALT, AST, TBL, and ALP should continue until levels normalize or return to approximate baseline levels.

Hepatic data should be collected in the event that 1 (or more) of the following conditions is met for the patient during the course of the study:

- elevation of serum ALT level to $\geq 10 \times$ ULN
- patients without liver tumors or liver metastasis: ALT $\geq 5 \times$ ULN and total bilirubin $\geq 2 \times$ ULN
- patients with liver tumors or liver metastasis: ALT $\geq 8 \times$ ULN and total bilirubin $\geq 2 \times$ ULN

- discontinuation from study treatment due to a hepatic event or abnormality of liver test results
- occurrence of a hepatic event considered to be an SAE

8.2.1.3. Venous Thromboembolic Event Assessment

If a patient develops clinical features of a DVT or PE, appropriate local laboratory tests and imaging should be performed as necessary for the diagnosis of the event. For confirmed cases, additional laboratory testing is recommended. Selected tests may be obtained in the event of a confirmed venous thromboembolic event and may be required in follow-up with patients in consultation with Lilly, its designee, or the Lilly designated medical monitor.

8.3. Adverse Events and Serious Adverse Events

Investigators are responsible for monitoring the safety of participants who have entered this study and for alerting Lilly or its designee to any event that seems unusual, even if this event may be considered an unanticipated benefit to the participant.

The investigator is responsible for the appropriate medical care of participants during the study.

Investigators must document their review of each laboratory safety report.

The investigator remains responsible for following, through an appropriate health care option, AEs that are serious or otherwise medically important, considered related to the investigational product or the study, or that caused the participant to discontinue the investigational product before completing the study. The participant should be followed until the event resolves, stabilizes with appropriate diagnostic evaluation, or is otherwise explained. The frequency of follow-up evaluations of the AE is left to the discretion of the investigator.

Lack of drug effect is not an AE in clinical studies because the purpose of the clinical study is to establish treatment effect.

After the ICF is signed, study site personnel will record via CRF the occurrence and nature of each participant's preexisting conditions, including clinically significant signs and symptoms of the disease under treatment in the study. In addition, site personnel will record any change in the condition(s) and any new conditions as AEs. Investigators should record their assessment of the potential relatedness of each AE to protocol procedure, investigational product, via CRF.

The investigator will interpret and document whether or not an AE has a reasonable possibility of being related to study treatment, study device, or a study procedure, taking into account the disease, concomitant treatment or pathologies.

A "reasonable possibility" means that there is a cause and effect relationship between the investigational product, study device, and/or study procedure and the AE.

The investigator answers yes/no when making this assessment.

Planned surgeries and nonsurgical interventions should not be reported as AEs unless the underlying medical condition has worsened during the course of the study.

If a participant's investigational product is discontinued as a result of an AE, study site personnel must report this to Lilly or its designee via CRF, clarifying if possible, the circumstances leading to any dosage modifications, or discontinuations of treatment.

Serious Adverse Events

An SAE is any AE from this study that results in 1 of the following outcomes:

- death
- initial or prolonged inpatient hospitalization
- a life-threatening experience (that is, immediate risk of dying)
- persistent or significant disability/incapacity
- congenital anomaly/birth defect
- important medical events that may not be immediately life-threatening or result in death or hospitalization but may jeopardize the participant or may require intervention to prevent 1 of the other outcomes listed in the definition above. Examples of such medical events include allergic bronchospasm requiring intensive treatment in an emergency room or at home, blood dyscrasias or convulsions that do not result in inpatient hospitalization, or the development of drug dependency or drug abuse.

All AEs occurring after signing the ICF are recorded in the CRF and assessed for serious criteria. The SAE reporting to the sponsor begins after the participant has signed the ICF and has received investigational product. However, if an SAE occurs after signing the ICF, but prior to receiving investigational product, the SAE should be reported to the sponsor as per SAE reporting requirements and timelines (see Section 8.3.1) if it is considered reasonably possibly related to study procedure.

Study site personnel must alert Lilly or its designee of any SAE within 24 hours of investigator awareness of the event via a sponsor-approved method. If alerts are issued via telephone, they are to be immediately followed with official notification on study-specific SAE forms. This 24-hour notification requirement refers to the initial SAE information and all follow-up SAE information. Participants with a serious hepatic AE should have additional data collected using the CRF.

Pregnancy (during maternal or paternal exposure to investigational product) does not meet the definition of an AE. However, to fulfill regulatory requirements, any pregnancy should be reported following the SAE process to collect data on the outcome for both mother and fetus.

Investigators are not obligated to actively seek AEs or SAEs in participants once they have discontinued and/or completed the study (the participant disposition CRF has been completed). However, if the investigator learns of any SAE, including a death, at any time after a participant has been discharged from the study, and he/she considers the event reasonably possibly related to the study treatment or study participation, the investigator must promptly notify Lilly.

Serious adverse events, including death, caused by disease progression should not be reported unless the investigator deems them to be possibly related to LY3435151, pembrolizumab, or the combination of LY3435151 and pembrolizumab.

Suspected Unexpected Serious Adverse Reactions

Suspected unexpected serious adverse reactions (SUSARs) are serious events that are not listed in the IB and that the investigator identifies as related to investigational product or procedure. United States 21 Code of Federal Regulations (CFR) 312.32 and European Union Clinical Trial Directive 2001/20/EC and the associated detailed guidances or national regulatory requirements in participating countries require the reporting of SUSARs. Lilly has procedures that will be followed for the identification, recording, and expedited reporting of SUSARs that are consistent with global regulations and the associated detailed guidances.

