6.6. Dose Modification

Dose reductions are not allowed in this study.

No dose modification for either LY3435151 or pembrolizumab (delays or omissions greater than 14 days) is allowed during the DLT observation period (42 days for Cohorts A1-A6 and B1-B2). Starting at Cycle 3, dose delays will be permitted. See Section 7 for discontinuation criteria.

After the DLT observation period, doses of the LY3435151 or pembrolizumab may be delayed, omitted, or discontinued to manage specific AEs or other toxicities. All dose modifications should be documented, including the approach taken and a clear rationale for the need for modification. The investigator must assess whether the toxicity is at least possibly due to study treatments and apply the dose modification guidelines. Investigators are encouraged to consult Lilly for additional guidance.

A cycle is defined as an interval of 21 days as shown in the SoA (Section 1.3). A delay of a cycle due to holiday, weekend, bad weather, or other unforeseen circumstances will be permitted for a maximum of 7 days and not counted as a protocol deviation. The reason for the delay should be documented on the eCRF.

Starting at Cycle 3, if a patient requires a cycle delay for any safety reasons other than those above, study treatment should be resumed within 21 days, if possible and appropriate. In rare circumstances, a cycle delay of >21 days may be permitted before permanent treatment discontinuation, as long as the patient demonstrates clinical benefit, does not have objective progression, and is recovering from the toxicity. Longer delays may be allowed for irAEs, as described in Section 6.6.1. Such circumstances must be discussed with the Lilly CRP/CRS.

Adverse events of immune-related etiology are expected because of the study drug's mechanism of action and may occur shortly after the first dose or several months after the last dose. Study treatment must be withheld if the patient experiences a drug-related toxicity or a severe or life-threatening AE.

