5.4.7. Safety Analyses

All patients who receive at least 1 dose of any study therapy will be evaluated for safety and toxicity.

Safety measures that will be used in the study include AEs, DLT (defined in protocol) in dose escalation phase, clinical laboratory test results and vital signs. The MedDRA Version 22.0 (or higher) will be used when reporting AEs by MedDRA terms. A treatment-emergent adverse event (TEAE) is defined as an event that first occurred or worsened in severity between the first dose of study treatment and 30 days after the last dose of study treatment and related serious AEs (SAEs) reported beyond 30 days after the last dose of study treatment. Immune-related adverse event (irAE) is also indicated in the database and will be summarized in the safety analysis.

Safety analyses will include summaries of the following:

- DLTs at each dose level in Part A and Part B
- AEs, including severity and possible relationship to the study drug
- DLT-equivalent AEs, including severity and possible relationship to the study drug
- SAEs, summarized by PT and repeated for events deemed by the investigator to be possibly related to study treatment

- irAEs, summarized by PT and repeated for events leading to dose delays or omissions, for events leading to discontinuations from study treatment, and for events leading to death
- AEs leading to dose delays or omissions, summarized by PT
- AEs leading to discontinuations from study treatment, summarized by PT and repeated for events deemed by the investigator to be possibly related to study treatment
- AEs leading to death, summarized by PT and repeated for events deemed by the investigator to be possibly related to study treatment
- reasons for deaths, summarized for all deaths, deaths on therapy, and deaths within 30 days of treatment discontinuation
- treatment-emergent abnormal changes in laboratory values
- treatment-emergent abnormal changes in vital signs and electrocardiograms
- Listings of all AEs, TEAEs, SAEs, and deaths will also be provided.
- Listings of all laboratory data will be provided with a flag for values outside of the laboratory normal. Abnormal results will be listed separately for all enrolled patients.

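### Protocol 8.3 defines a reasonable possibility of relatedness as an actual causal link, which contradicts the possibility-level safety summaries in Protocol 9.4.4 and SAP 5.4.7

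*Protocol*

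**What the plan says.** Protocol Section 8.3 asks the investigator to document "whether or not an AE has a reasonable possibility of being related to study treatment, study device, or a study procedure". The next paragraph explains the key term: a reasonable possibility "means that there is a cause and effect relationship between the investigational product, study device, and/or study procedure and the AE". The response scale is binary: "The investigator answers yes/no when making this assessment". There is no intermediate category.

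Earlier in the same section, investigators are told to record the *potential* relatedness of each AE. Other sections also work at the level of possibility:

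- Protocol 6.6 on dose modification: "The investigator must assess whether the toxicity is at least possibly due to study treatments".
- Protocol 9.4.4: AE and SAE summaries by *possible* relationship to study drug.
- SAP 5.4.7: "SAEs, summarized by PT and repeated for events deemed by the investigator to be possibly related to study treatment". It specifies the same repetition for AEs leading to discontinuation and AEs leading to death.

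Two places use plain *related*, with no qualifier of their own. The TEAE definition in SAP 5.4.7 extends past 30 days only for "related serious AEs (SAEs) reported beyond 30 days after the last dose of study treatment". The SUSAR paragraph in Protocol 8.3 covers serious events not listed in the IB "that the investigator identifies as related to investigational product or procedure".

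**The concern.** The definition contradicts the term it defines. A clinician who thinks the drug may have contributed, but cannot show it, would answer yes to the question and no under its definition. The scale leaves nowhere else to put the event.

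This matters because events of uncertain cause are to be expected here. LY3435151 is a new agent, given in some cohorts with a second immunotherapy, to patients with advanced cancer. Protocol 6.6 and 6.6.1 also warn that immune-related events may appear several months after the last dose, so serious events after day 30 are foreseeable. If sites follow the definition, summaries labelled *possibly related* would hold only events with an established cause. If sites differ in their reading, one variable would mix two standards.

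**Working it through.** No sample size, power or interval figure depends on this definition. The plan's only figures on AE incidence are the Clopper-Pearson limits in Protocol 9.2 and SAP Table JZIA.5.1. All ten rows reproduce to two decimals, but they take the count as given and do not bear on how it is formed. The check is therefore a trace of the text.

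**Step 1: which standard governs the yes/no field?** The question itself and *potential relatedness* point to possibility; the explicit definition points to established cause. No section says which prevails.

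**Step 2: which outputs depend on the answer?**

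| Output | Test stated there | If 8.3 is applied literally |
|---|---|---|
| Related-AE and related-SAE summaries (Protocol 9.4.4, SAP 5.4.7) | possible relationship / possibly related, by investigator judgement | Lower; contents no longer match the label |
| SAEs more than 30 days after last dose, as TEAEs (SAP 5.4.7) | related | Uncertain-cause events leave the TEAE set |
| SUSAR trigger (Protocol 8.3) | related, as identified by the investigator | Narrower at the investigator step |
| All-cause AE and SAE tables, SAE listings | none | Unchanged |
| SAE collection in short-term follow-up (Protocol 1.3): 90 days, or 30 days after cessation if new anticancer treatment starts | none | Unchanged |
| DLTs, hence mTPI-2 decisions (Protocol 4.1.1.2) | counted unless clearly and directly due to disease or another cause; the catch-all item says possibly related | Unchanged |
| Pre-dose SAEs (Protocol 8.3, 8.3.1) | reasonably possibly related to study procedure | Own test |
| SAEs caused by progression (Protocol 8.3, 8.3.1) | "unless the investigator deems them to be possibly related to LY3435151, pembrolizumab, or the combination" in 8.3; similar in 8.3.1 | Own test |

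For SAEs learned of after discharge, 8.3 says *reasonably possibly related* and 8.3.1 says *reasonably related*. The wording varies, so I do not count these either way.

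**Step 3: direction and size.** In a group of *n* treated patients, let *a* have at least one event of established cause and *u* have only events of uncertain cause. Let *s* be the share of those *u* patients whose events are all answered no.

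- Possibility-level rate: (a + u)/n.
- Reported rate: (a + (1 − s)u)/n.
- Shortfall: s·u/n, between 0 (s = 0) and u/n (s = 1).

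The shortfall cannot be negative, so the error runs one way. The documents give neither *u* nor *s*. They do give the planned group sizes, so the effect of one reclassified patient follows:

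- C1 or C2 (16 randomised 1:1, so 8): 1/8 = 12.5 percentage points.
- D1 or D2 at the interim review (20): 1/20 = 5 points.
- D3 (30): 1/30 = 3.3 points.
- D1 or D2 in full (40): 1/40 = 2.5 points.

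How many patients would be reclassified is unknown and may be none.

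**The case against.** The strongest reply is that Section 8.3, read as a whole, contains two possibility-level statements and one badly phrased gloss, so experienced sites would apply possibility. The summaries are themselves labelled *possible* or *possibly related*, and the CRF instructions, which are not among the documents, may already say so. This stands as a limit: the loss is conditional. It does not remove the contradiction, because the only explicit definition of the term is the strict one.

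Stronger readings are tempting, and the documents do not support them.

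- *Events of uncertain cause are certain to be lost.* Sites may follow either standard.
- *The rest of the plan uses possibility throughout.* It does not. Besides the unqualified wording noted above, Protocol 8.3.1 and Appendix 3 say *reasonably related*.
- *Dose finding or the primary endpoints are compromised.* DLTs have their own exclusion-based test, and the primary endpoints are not defined by relatedness. The one route into them is the late-SAE clause of the TEAE definition. A late SAE answered no leaves the TEAE count but stays in the SAE data and listings.
- *Expedited reporting will fall short.* After dosing, SAEs go to the sponsor within 24 hours whatever the causality answer, apart from progression-caused events, which have their own test. Protocol 8.2 provides for at least quarterly cumulative SAE review. Protocol 8.3 says the sponsor's own SUSAR procedures are consistent with global regulations. Those procedures are not shown, so only the investigator's step can be said to narrow.

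**Conclusion.** The point holds as an internal contradiction in an operative rule, with conditional consequences. It is more than a clerical slip, because the sentence governs how a reported variable is filled in. If sites apply it literally, three outputs are affected: the related-AE and related-SAE summaries, late SAEs within the TEAE set, and the investigator-based SUSAR trigger. The direction is towards fewer related events. The size is indeterminate: from zero, if every site reads the section as possibility, up to every patient whose only related events are of uncertain cause. The conclusion assumes that the yes/no answer feeds the relatedness summaries, which is the natural reading of Protocol 8.3 with SAP 5.4.7, and that the CRF instructions do not already correct the definition.

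**What to change.** In Protocol 8.3, reword the definition so that a reasonable possibility means there *may be* a cause and effect relationship between the product, device or procedure and the AE. Carry the same wording into the CRF instructions. The yes/no field then uses the same standard as the summaries in Protocol 9.4.4 and SAP 5.4.7, and the plain *related* in the TEAE and SUSAR text takes its meaning from it. The SAP needs no change. A further rule that every uncertain event must be answered yes would go beyond reconciling the text and is not needed.

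The cost is one sentence in the protocol and the matching line in the CRF instructions. The downside is that reported related-event rates may be somewhat higher. The change is best made before data accrue, because relatedness is hard to re-judge afterwards.
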